#### **7.6.10.4 Additional Analyses**

In addition, further analyses on specific laboratory parameters will be performed by treatment group:

##### Abnormal Hepatic Function Test

The number of subjects with the following laboratory abnormalities from on-treatment evaluations will be summarized by treatment group:

- ALT or AST > 3 x ULN, > 5 x ULN, > 10 x ULN and > 20 x ULN
- Total bilirubin > 2 x ULN
- Concurrent (within 1 day) ALT or AST > 3 x ULN and total bilirubin > 2 x ULN
- Concurrent (within 30 days) ALT or AST > 3 x ULN and total bilirubin > 2 x ULN

The analyses will be conducted using the 30-day safety window.

A by-subject listing of these specific abnormalities will be provided.

##### Abnormal Thyroid Function Test

The number of subjects with the following laboratory abnormalities from on-treatment evaluations will be summarized by treatment group:

- TSH value > ULN and
  - with baseline TSH value  $\leq$  ULN
  - with at least one FT3/FT4 test value < LLN within 2-week window after the abnormal TSH test
  - with all FT3/FT4 test values  $\geq$  LLN within 2-week window after the abnormal TSH test
  - with FT3/FT4 missing within 2-week window after the abnormal TSH test.
- TSH < LLN and
  - with baseline TSH value  $\geq$  LLN
  - with at least one FT3/FT4 test value > ULN within 2-week window after the abnormal TSH test
  - with all FT3/FT4 test values  $\leq$  ULN within 2-week window after the abnormal TSH test
  - with FT3/FT4 missing within 2-week window after the abnormal TSH test

The analyses will be conducted using the 30-day safety window.

A by-subject listing of these specific abnormalities will be provided.

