Laboratory Tests	X	On site/local complete blood count (CBC) w/differential, chemistry panel including: LDH, AST, ALT, ALP, total bilirubin, blood urea nitrogen (BUN) or serum urea level, creatinine, Ca, Na, K, Cl, fasting glucose and albumin within 14 days prior to randomization. Endocrine panel (TSH, Free T4, Free T3; Total T3/T4 are acceptable if Free T3/T4 are not available), Hep B/C (HBV HBsAG, HCV antibody or HCV RNA), within 28 days prior to randomization.			
Pregnancy Test (WOCBP only)	X	Serum or urine to be done at screening visit and repeated within 24 hours prior to first dose of study drug.			
Efficacy Assessment		·			
Baseline Tumor Imaging Assessment	X	CT/MRI scan of chest, abdomen, pelvis and any clinically indicated sites within 28 days prior to randomization. CT/MRI scan prior to ICF signature might be acceptable if performed within 28 days prior to randomization.			
IRT					
IRT contact	X	The IRT must be contacted for subject number assignment at the time informed consent is obtained.			

Table 5.1-2: On	Table 5.1-2: On-Treatment Assessments - Subjects in Nivolumab-plus-Ipilimumab Arm (CA209649)				
Procedure	Cycle 1 Day 1 (3-week cycle) C1D1	Cycles 2 - 4 (Every 3 weeks) on Day 1	Cycle 5 and beyond (Every 2 weeks) on Day 1 ^a	Note *Treatment till PD, unacceptable toxicity, withdraw from IC	
Safety Assessments					
Physical Examination	X	X	X	To be performed within 72 hours of dosing.	
Vital Signs	X	X	X	Obtain vital signs within 72 hours prior to dose. Including BP, heart rate, and temperature.	
Weight and ECOG Performance Status	X	X	X	Within 72 hours of dosing. See protocol Appendix 3 for ECOG Performance Status scale.	
Adverse Events Assessment		Continuously		Assessed using NCI CTCAE v.4	
Serious Adverse Event (SAE)		Continuously		Assessed using NCI CTCAE v.4	
Review of concomitant medications	X	X	X	-	
Laboratory Tests	See Note	See Note	See Note	Within 72 hours prior to each dose through Week 23 visit and every alternate dose thereafter.	
				Include CBC w/differential, ALT, AST, total bilirubin, BUN or serum urea level, creatinine, Ca, Na, K, Cl, LDH and glucose.	
				TSH (with reflexive Free T4 and Free T3; Total T3/T4 are acceptable if Free T3/T4 are not available) every 6 weeks (± 7 days) starting at C1D1.	
				Note: Laboratory tests do not need to be repeated on C1D1 if performed within 14 days prior to first dose.	

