Table 5.1-3: On-Treatment Assessments - Subjects in Nivolumab-plus-Chemotherapy (XELOX or FOLFOX) Arm (CA209649)Nivolumab-Nivolumab-plusplus-XELOX Nivolumab-plus-**FOLFOX** and XELOX Note Cycle 2 and Nivolumab-Cycle 2 and **Procedure** *Treatment till PD, unacceptable toxicity, withdraw bevond beyond plusfrom IC (Every 2 weeks) **FOLFOX** (Every 3 weeks) on Day 1^a on Day 1 Cycle 1 Day 1 (C1D1)**Safety Assessments** X X X **Targeted Physical Examination** To be performed within 72 hours of dosing. X X Vital Signs X Obtain vital signs within 72 hours prior to dose. Including BP, heart rate and temperature. Weight, BSA and ECOG X X X Within 72 hours of dosing. See protocol Appendix 3 for Performance Status ECOG Performance Status scale Adverse Events Assessment Continuously Assessed using NCI CTCAE v.4 Assessed using NCI CTCAE v.4 Serious Adverse Event (SAE) Continuously Review of concomitant X X X medications Nivolumab + XELOX: Within 72 hours prior to each Laboratory Tests See Note See Note See Note dose. Nivolumab + FOLFOX: Within 72 hours prior to each dose through Week 23 and every alternate dose thereafter. Include CBC w/differential, ALT, AST, total bilirubin, BUN or serum urea level, creatinine, Ca, Na, K, Cl, LDH and glucose. TSH (with reflexive Free T4 and Free T3; Total T3/T4 are acceptable if Free T3/T4 are not available) every 6 weeks (\pm 7 days) starting at C1D1. Note: Laboratory tests do not need to be repeated on C1D1 if performed within 14 days prior to first dose.

Table 5.1-3: On-Treatment Assessments - Subjects in Nivolumab-plus-Chemotherapy (XELOX or FOLFOX) Arm (CA209649)					
Procedure	and XELOX FOL Cycle 2 and beyond beyond FOLFOX (Every 3 weeks)		Nivolumab-plus- FOLFOX Cycle 2 and beyond (Every 2 weeks) on Day 1 ^a	Note *Treatment till PD, unacceptable toxicity, withdraw from IC	
Pregnancy Test (WOCBP only)	X	See Note	See Note	Serum or urine within 24 hours prior to the initial administration of study drug and then every 4 weeks (± 7 days) regardless of dose delays; if collected with a dosing visit, then obtain within 24 hours prior to administration of study drug: urine or serum.	
PK and Immunogenicity Sampling					
PK samples	See Table 5.5-2 and Table 5.5-3 for details regarding specific sample timing.				
Immunogenicity blood sample		See Table 5.5-2 and Table 5.5-3 for details regarding specific sample timing.			

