Review of concomitant medications	X	X	X	-		
Laboratory Tests	See Note	See Note	See Note	XELOX: Within 72 hours prior to each dose. FOLFOX: Within 72 hours prior to each dose through Week 23 and every alternate dose thereafter. Include CBC w/differential, ALT, AST, total bilirubin, BUN or serum urea level, creatinine, Ca, Na, K, Cl, LDH and glucose. Note: Laboratory tests do not need to be repeated on C1D1 if performed within 14 days prior to first dose.		
Pregnancy Test (WOCBP only)	X	See Note	See Note	Serum or urine within 24 hours prior to the initial administration of study drug and then every 4 weeks (± 7 days) regardless of dose delays; if collected with a dosing visit, then obtain within 24 hours prior to administration of study drug: urine or serum.		

Table 5.1-4: On-Treatment Assessments - Subjects in Chemotherapy (XELOX or FOLFOX) Arm (CA209649)					
Procedure	FOLFOX Cycle 1 Day 1 (C1D1) Cycle 2 and beyond (Every 3 weeks) (Every 3 weeks)		FOLFOX Cycle 2 and beyond (Every 2 weeks) on Day 1	Note *Treatment till PD, unacceptable toxicity, withdraw from IC	
Efficacy Assessments					
Tumor Imaging Assessment		See Note	See Note	CT/MRI scan of chest, abdomen, pelvis, and any clinically indicated sites.	
				Every 6 weeks (± 7 days) from first dose up to and including Week 48, then every 12 weeks (± 7 days) regardless of treatment schedule until disease progression or the subject withdraws consent, whichever comes first. Subjects who discontinue study treatment for reasons other than PD will continue to have tumor assessments until their disease progresses or they withdraw consent. Use same imaging method as was used at screening/baseline	
Collection of biomarker sampling data					
Outcomes Research Assessments					
FACT-Ga	X			Assessed every 6 weeks (± 3 days) from C1D1,	
EQ-5D-3L	X	See Note	See Note	regardless of treatment schedule; if administered on a dosing day, assessment should take place prior to any other study procedures.	
Health Care Resource Utilization	X	X	X		

Table 5.1-4: On-Treatment Assessments - Subjects in Chemotherapy (XELOX or FOLFOX) Arm (CA209649)					
Procedure	XELOX and FOLFOX Cycle 1 Day 1 (C1D1)	XELOX Cycle 2 and beyond (Every 3 weeks) on Day 1	FOLFOX Cycle 2 and beyond (Every 2 weeks) on Day 1	Note *Treatment till PD, unacceptable toxicity, withdraw from IC	
Study Drug					
Randomization	X			Contact IRT for randomization	

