### **7.1.1.3 Immune-Mediated Adverse Events (US Submission)**

In order to further characterize AEs of special clinical interest, analysis of immune-mediated AEs (IMAE) will be conducted. IMAEs are specific events (or groups of PTs describing specific events) that include pneumonitis, diarrhea/colitis, hepatitis, nephritis/renal dysfunction, rash, endocrine (adrenal insufficiency, hypothyroidism/thyroiditis, hyperthyroidism, diabetes mellitus, and hypophysitis), and other specific events, considered as potential immune-mediated events by investigator that meet the definition summarized below:

- those occurring within 100 days of the last dose,
- regardless of causality,
- treated with immune-modulating medication (of note, endocrine AEs such as adrenal insufficiency, hypothyroidism/thyroiditis, hyperthyroidism, diabetes mellitus, and hypophysitis are considered IMAEs regardless of immune-modulating medication use, since endocrine drug reactions are often managed without immune-modulating medication).
- with no clear alternate etiology based on investigator assessment, or with an immune-mediated component

The list of MedDRA preferred terms used to identify IMAEs is revisited quarterly and updated accordingly. The preferred terms used for the selection at the time of the database lock by categories will be provided.

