## **7.6 Safety**

Analyses in this section will be tabulated for all treated subjects by treatment group as treated, unless otherwise specified. In addition some safety selected outputs will be presented for treated CPS  $\geq$  5 Subjects.

For chemotherapy (FOLFOX or XELOX) the Chemotherapy regimen “as treated” will be reported (see [Section 6.2](#)).

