### **7.6.10 Laboratory Parameters**

The analysis population for each laboratory test is restricted to treated subjects who underwent that laboratory test.

A by-subject listing of differences in categorization of SI and US laboratory test results will be provided.

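### The thyroid laboratory table sets arms side by side although Table 5.1-4 schedules no on-treatment thyroid test for chemotherapy, so its columns are not comparable if that table governs

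*SAP*

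**What the plan says.** **The analysis.** Under abnormal thyroid function tests, SAP 7.6.10.4 states: "The number of subjects with the following laboratory abnormalities from on-treatment evaluations will be summarized by treatment group". The chemotherapy arm is included, because SAP 7.6 says: "Analyses in this section will be tabulated for all treated subjects by treatment group as treated, unless otherwise specified". The denominator comes from SAP 7.6.10: "The analysis population for each laboratory test is restricted to treated subjects who underwent that laboratory test". SAP 7.1 makes frequency plus proportion the default for categorical summaries. The thyroid section says nothing about unequal testing.

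**The schedules.**
- Table 5.1-2 (nivolumab plus ipilimumab): "Total T3/T4 are acceptable if Free T3/T4 are not available) every 6 weeks (± 7 days) starting at C1D1".
- Table 5.1-3 (nivolumab plus chemotherapy): the same requirement, "Total T3/T4 are acceptable if Free T3/T4 are not available) every 6 weeks".
- Table 5.1-4 (chemotherapy): the list runs straight from glucose to the Cycle 1 note, "Na, K, Cl, LDH and glucose. Note: Laboratory tests do not need to be repeated on C1D1", with no TSH, T3 or T4.
- Table 5.1-5 (follow-up, all arms): "Include CBC w/differential, ALT, AST, total bilirubin, BUN or serum urea level, creatinine, Ca, Na, K, Cl, LDH and glucose", again with no thyroid test.

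**The text that does not match.** Protocol 5.3.2 sets thyroid testing every 6 weeks from Cycle 1 Day 1 without naming an arm. Its parenthesis translates this into cycles for nivolumab regimens only. The same section allows tests outside the schedule when there is a clinical reason or when local rules require them.

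**The concern.** A side-by-side table invites the reader to compare columns. That comparison needs similar detection in each arm. Here detection appears to be systematic in the nivolumab arms and opportunistic in the control arm. Two distortions follow, and they run in opposite directions. Cases that nobody looked for are missing from the chemotherapy count. The subjects who were tested are probably enriched for suspected disease, which raises the percentage among those tested. Thyroid dysfunction is one of the endocrine events that SAP 7.1.1.3 singles out for analysis, so a misleading control column affects a safety comparison that readers will look at.

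The same unequal detection can reach the endocrine adverse event tables. SAP 7.1.1.3 says that endocrine events "are considered IMAEs regardless of immune-modulating medication use", and SAP 7.6.6 and 7.6.7 include any-grade columns. Low-grade events that come to light through a blood test are more likely to be found where the test is scheduled.

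**Working it through.** The plan gives no figure to reproduce, so the check is a comparison of passages, a count of scheduled tests, and an illustration with assumed inputs.

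**1. Can the screening panel fill the gap?** No. Table 5.1-1 requires a thyroid panel for all subjects within 28 days before randomization, which gives each arm a baseline. SAP 6.1 counts a laboratory result as on-treatment only if it was taken after first dosing.

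**2. Can the follow-up visits fill it?** No. Table 5.1-5 lists no thyroid test in any arm.

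**3. Scheduled on-treatment tests per subject.** Formula: weeks on treatment divided by 6, rounded down, not counting Cycle 1 Day 1.
- Week 24: 24/6 = 4 in a nivolumab arm, 0 on chemotherapy under Table 5.1-4.
- Week 48: 48/6 = 8, against 0.
- Week 104: 104/6 = 17.3, so 17, against 0.

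These counts are for subjects who stay on two- or three-weekly dosing. They are somewhat lower after a move to four-weekly dosing, where thyroid testing goes with every second dose.

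**4. Contrast with the hepatic table.** SAP 7.6.10.4 uses the same sentence for hepatic tests. ALT, AST and bilirubin are scheduled in all three on-treatment tables, so the same layout is sound there.

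**5. Illustration (all inputs assumed).** Let p be the true incidence, equal in both arms, and let scheduled testing find every case. On chemotherapy, let a be the probability that a case is tested and b the probability that a non-case is tested. Then:
- share of treated subjects shown as abnormal = p × a
- share tested = p × a + (1 − p) × b
- percentage among those tested = p × a / [p × a + (1 − p) × b]

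Worked line, p = 0.10, a = 0.50, b = 0.10: 0.10 × 0.50 = 0.050; tested = 0.050 + 0.90 × 0.10 = 0.140; 0.050/0.140 = 35.7%.

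| p (shown in the scheduled arm) | a | b | Chemotherapy, % of treated | Chemotherapy, % of tested |
|---|---|---|---|---|
| 5% | 0.20 | 0.05 | 1.0 | 17.4 |
| 5% | 0.50 | 0.10 | 2.5 | 20.8 |
| 5% | 0.80 | 0.10 | 4.0 | 29.6 |
| 5% | 0.50 | 0.50 | 2.5 | 5.0 |
| 10% | 0.20 | 0.05 | 2.0 | 30.8 |
| 10% | 0.50 | 0.10 | 5.0 | 35.7 |
| 10% | 0.80 | 0.10 | 8.0 | 47.1 |
| 10% | 0.50 | 0.50 | 5.0 | 10.0 |

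Whenever testing depends on disease (a > b), the percentage among those tested exceeds the true incidence, while the count falls short by the factor a. Only when a = b is the percentage right, and the count is then still halved at a = 0.50.

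**The case against.** **Protocol 5.3.2 may cover every arm.** The section concerns anyone who received study drug, and its main clause names no arm. If it governs, scheduled control data exist and suppressing the chemotherapy percentage would discard valid information. This stands, and it makes the point conditional. The nivolumab-only cycle counts favor the reading in Table 5.1-4 but do not settle it.

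**Unscheduled does not mean for-cause.** A reader might infer that every chemotherapy test was prompted by symptoms. Protocol 5.3.2 also allows tests under local rules, so selective testing is likely but not certain.

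**A TSH abnormality is not automatically an adverse event.** A reader might infer that low-grade thyroid events are found only where TSH is scheduled. The documents do not support that. Unscheduled tests occur in any arm. Protocol 6.3 asks for laboratory abnormalities to be recorded when they are clinically significant, serious, lead to interruption or discontinuation, or need corrective therapy. SAP 7.1.1.3 also requires the investigator to consider the event potentially immune-mediated. More likely to be found is as far as one can go.

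**Severity breakdowns are already planned.** SAP 7.6.5 tabulates adverse events by preferred term and each worst grade from 1 to 5, so an added Grade 2 or higher row would largely re-cut existing output. It is not needed.

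**It is a descriptive display.** No test or decision uses the table. SAP 7.6.10.4 asks for numbers of subjects, and percentages come from the general default. The mock-ups sit in a Data Presentation Plan that is not among the documents and may already show the number tested. Because SAP 7.1 keeps the two comparisons separate, removing chemotherapy altogether would leave a one-column table. This limits the weight of the point and favors labeling the column over deleting it.

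**Conclusion.** The point holds conditionally and is minor. As written, Table 5.1-4 and protocol 5.3.2 do not agree on whether chemotherapy subjects have scheduled thyroid tests, and the SAP does not address the difference. If Table 5.1-4 governs, the chemotherapy column rests on unscheduled tests alone, against 4 scheduled tests by week 24 and 8 by week 48 in the nivolumab arms. Its count is then likely too low and its tested-only percentage likely too high.

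The documents give no testing or abnormality rates for chemotherapy, so the size of the bias cannot be stated. Under the assumed settings with disease-dependent testing, a true 10% would appear as 2.0% to 8.0% of treated subjects and 30.8% to 47.1% of those tested. A true 5% would appear as 1.0% to 4.0% and 17.4% to 29.6%. These ranges assume equal true incidence and complete detection under scheduled testing; they show direction and possible scale and do not predict the result. No error rate or efficacy conclusion is touched.

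**What to change.** 1. Reconcile protocol 5.3.2 with Table 5.1-4, and record in the SAP which schedule applied to chemotherapy subjects.
2. If Table 5.1-4 applied, then in the thyroid laboratory table:
   - show the number of subjects tested in each arm;
   - give the chemotherapy arm as a count without a percentage, or mark that column as not comparable;
   - footnote that Table 5.1-4 schedules no on-treatment thyroid test.
3. Put the same detection caveat on the any-grade endocrine select adverse event and immune-mediated adverse event tables.

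This changes table shells and footnotes only, with no new tests or data. The cost is that no chemotherapy percentage is shown for thyroid laboratory values. SAP version 5.0 notes that the report for nivolumab plus chemotherapy has been written. SAP Section 10 places the nivolumab plus ipilimumab report at the second analysis time point, so the change can still be made there.

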#### **7.6.11 Vital Signs**

Vital signs will be listed by subject.

#### **7.6.12 Physical Measurements**

Physical measurements will be listed by subject.

### **7.6.13 Immunogenicity Analysis**

Further details on immunogenicity background and rationale, definitions, population for analyses and endpoints are described in [APPENDIX 3](#).

#### **Incidence of ADA**

Number (%) of subjects will be reported for the following parameters based on nivolumab treated subjects with baseline and at least one post-baseline assessment. For the nivo +chemo arm the following parameters will be reported for nivolumab and for the nivolumab + ipilimumab arm the following parameters will be reported for nivolumab and ipilimumab.

- Baseline ADA-positive
- ADA-positive
  - Persistent Positive (PP)
  - Not PP-Last Sample Positive
  - Other positive
  - Neutralizing Positive
- ADA-negative

A listing of all ADA assessments will be provided together with results for neutralizing antibody.

A spider plot of nivolumab ADA test result (titers) over time may be provided for nivolumab ADA positive subjects.

#### **Clinical implications**

Clinical implications of nivolumab or ipilimumab immunogenicity will be primarily focused on subjects with persistent ADA-positive relative to ADA-negative. Subjects with any ADA-positive samples after initiation of treatment (relative to baseline) may be used to explore clinical implications. Effect of immunogenicity on clearance of nivolumab or ipilimumab will be explored by comparison of clearance estimates (determined by PPK analysis). Effect of immunogenicity on safety will be explored by examining the frequency and type of AEs of special interest such as hypersensitivity/infusion reaction. Summary tables for incidence of overall and each of the preferred terms will be provided, if the number of subjects is of sufficient size (eg, at least 10 subjects). Otherwise, individual subject's safety profile will be examined and described based on a listing. Clinical implications on efficacy will also be explored similarly. Association between trough concentrations of nivolumab or combination drug (eg, ipilimumab) and ADA assessments may be explored, as needed.

The following data presentation will be provided:

- Swimmer plot of occurrence of ADA and NAb Occurrence in Relation to PFS per BICR, BOR per BICR and OS

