- For future infusions, the following prophylactic premedications are recommended: diphenhydramine 50 mg (or equivalent) and/or acetaminophen/paracetamol 325 to 1000 mg should be administered at least 30 minutes before nivolumab or ipilimumab infusions. If necessary, corticosteroids (up to 25 mg of hydrocortisone or equivalent) may be used.

For Grades 3 or 4 symptoms: (severe reaction, Grade 3: prolonged [ie, not rapidly responsive to symptomatic medication and/or brief interruption of infusion]; recurrence of symptoms following initial improvement; hospitalization indicated for other clinical sequelae (eg, renal impairment, pulmonary infiltrates). Grade 4: Life-threatening; pressor or ventilatory support indicated):

• Immediately discontinue infusion of nivolumab or ipilimumab. Begin an IV infusion of normal saline and treat the subject as follows: Recommend bronchodilators, epinephrine 0.2 to 1 mg of a 1:1000 solution for subcutaneous administration or 0.1 to 0.25 mg of a 1:10,000 solution

injected slowly for IV administration, and/or diphenhydramine 50 mg IV with methylprednisolone 100 mg IV (or equivalent), as needed. Subject should be monitored until the Investigator is comfortable that the symptoms will not recur. Nivolumab or ipilimumab will be permanently discontinued. Investigators should follow their institutional guidelines for the treatment of anaphylaxis. Remain at bedside and monitor subject until recovery of the symptoms.

In case of late-occurring hypersensitivity symptoms (eg, appearance of a localized or generalized pruritus within 1 week after treatment), symptomatic treatment may be given (eg, oral antihistamine or corticosteroids.

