Study Cycle/Day Nivolumab + XELOX= every 3 weeks	Event (Relative to Start of Nivolumab Infusion)	Time (Relative to Start of Nivolumab Infusion) Hour:Min	Nivolumab PK Blood Sample	Nivolumab IMG Blood Sample
Cycle 1 Day 1	Predose ^a	00:00	X	X
Cycle 2 Day 1	Predose ^a	00:00	X	X
Cycle 5 Day 1	Predose ^a	00:00	X	X
Cycle 11 Day 1	Predose ^a	00:00	X	X
Cycle 17 Day 1	Predose ^a	00:00	X	X
Cycle 25 Day 1	Predose ^a	00:00	X	X
Cycle 33 Day 1	Predose ^a	00:00	X	X

Table 5.5-3: Pharmacokinetic and Immunogenicity Sampling Schedule for the Nivolumab + Chemotherapy Arm - Q2W Dosing with FOLFOX

Study Cycle/Day Nivolumab + FOLFOX= every 2 weeks	Event (Relative to Start of Nivolumab Infusion)	Time (Relative to Start of Nivolumab Infusion) Hour:Min	Nivolumab PK Blood Sample	Nivolumab IMG Blood Sample
Cycle 1 Day 1	Predose ^a	00:00	X	X
Cycle 2 Day 1	Predose ^a	00:00	X	X
Cycle 3 Day 1	Predose ^a	00:00	X	X
Cycle 7 Day 1	Predose ^a	00:00	X	X
Cycle 9 Day 1	Predose ^a	00:00	X	X
Cycle 17 Day 1	Predose ^a	00:00	X	X
Cycle 25 Day 1	Predose ^a	00:00	X	X
Cycle 37 Day 1	Predose ^a	00:00	X	X
Cycle 49 Day 1	Predose ^a	00:00	X	X

^a All predose samples should be taken just prior to the start of nivolumab infusion (preferably within 30 minutes). If nivolumab is discontinued, then PK and IMG samples should be collected for the next 2 cycles scheduled for PK/IMG sampling following discontinuation.

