#### **7.5.2.8 Analysis of OS by Tumor Response:**

Survival by response category will be analyzed by arm using the landmark method. Subjects still on study at the landmark time will be separated into two response categories according to whether they have responded before that time. This will assess whether survival from the landmark depends

on the subject's response status at the landmark. Subjects who go off protocol (eg, subjects who die) before the time of landmark will be excluded from the analysis.

The survival curves from Week 6, Week 12, Week 18, Month 6, Month 9, Month 12, by response status, for each randomized arm will be produced using the KM product-limit method. Two sided, 95% CIs for median OS will be constructed based on a log-log transformed CI for the survivor function  $S(t)$ .

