#### Subject ADA Status:

- Baseline ADA-positive subject: A subject with baseline ADA-positive sample
  - ADA-positive subject: A subject with at least one ADA positive-sample relative to baseline at any time after initiation of treatment
- 1) *Persistent Positive (PP)*: ADA-positive sample at 2 or more consecutive time points, where the first and last ADA-positive samples are at least 16 weeks apart
  - 2) *Not PP-Last Sample Positive*: Not persistent positive with ADA-positive sample at the last sampling time point

- 3) Other Positive: Not persistent positive but some ADA-positive samples with the last sample being negative
- 4) Neutralizing Positive: At least one ADA-positive sample with neutralizing antibodies detected
- **ADA-negative subject:** A subject with no ADA-positive sample after the initiation of treatment.

(Note: 16 weeks was chosen based on a long half-life of IgG4.)

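### The main ADA comparison in SAP 7.6.13 (persistent-positive vs ADA-negative) requires the positive group to be alive and sampled at Week 25 to 33, so any efficacy comparison on it is biased in favour of persistent-positive subjects

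*SAP*

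**What the plan says.** SAP 7.6.13 sets the main contrast: "Clinical implications of nivolumab or ipilimumab immunogenicity will be primarily focused on subjects with persistent ADA-positive relative to ADA-negative". It illustrates safety with hypersensitivity and infusion reactions, and then adds: "Clinical implications on efficacy will also be explored similarly". A comparison using any ADA-positive subject is permitted but not required.

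SAP Appendix 3 defines the groups:
- Persistent positive: "ADA-positive sample at 2 or more consecutive time points, where the first and last ADA-positive samples are at least 16 weeks apart".
- ADA-positive: "A subject with at least one ADA positive-sample relative to baseline at any time after initiation of treatment".
- ADA-negative: "A subject with no ADA-positive sample after the initiation of treatment". No minimum length of sampling is attached. A baseline sample and one post-baseline sample make a subject evaluable.

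The sampling visits are in Protocol 5.5: Table 5.5-1 for nivolumab plus ipilimumab (N+I), Table 5.5-2 for nivolumab plus XELOX, and Table 5.5-3, titled "Pharmacokinetic and Immunogenicity Sampling Schedule for the Nivolumab + Chemotherapy Arm - Q2W Dosing with FOLFOX". The notes to Tables 5.5-2 and 5.5-3 ask for samples at the next two scheduled sampling cycles after nivolumab stops. No such note appears under Table 5.5-1.

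For Grade 3 or 4 infusion reactions, Protocol 4.5.1.8 says: "Nivolumab or ipilimumab will be permanently discontinued".

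Elsewhere, where status also depends on surviving long enough to acquire it, the SAP does allow for this. In SAP 7.5.2.8: "Survival by response category will be analyzed by arm using the landmark method". SAP 7.5.3.4 does the same for N+I. Section 7.6.13 names no landmark and no time-dependent status.

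**The concern.** The two groups are defined on different clocks. ADA-negative status can be reached at Week 3 or 4 and kept by a subject who dies the next week. Persistent-positive status has to be earned by surviving and giving samples for months. The time before it can be earned is event-free by construction in one group and not in the other, which is immortal-time bias. Persistent-positive subjects would then appear to do better on OS, PFS or response even if ADA had no effect, and a real loss of efficacy could look like no effect or even benefit.

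The safety contrast has a related gap. An ADA-positive subject who stops early, including after a severe infusion reaction, may be classed as last-sample-positive or other-positive and so fall outside the main comparison.

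**Working it through.** **Step 1. Visit weeks.** Week = 1 + cycle length × (cycle − 1). For N+I from Cycle 5, week = 13 + 2 × (cycle − 5).

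| Schedule | Sampled cycles | Weeks |
|---|---|---|
| N+I, nivolumab ADA | 1, 2, 4, 5, 11, 17, 23, 35, 47 | 1, 4, 10, 13, 25, 37, 49, 73, 97 |
| N+I, ipilimumab ADA | 1, 2, 4, 5, 11 | 1, 4, 10, 13, 25 |
| Nivolumab + XELOX | 1, 2, 5, 11, 17, 25, 33 | 1, 4, 13, 31, 49, 73, 97 |
| Nivolumab + FOLFOX | 1, 2, 3, 7, 9, 17, 25, 37, 49 | 1, 3, 5, 13, 17, 33, 49, 73, 97 |

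**Step 2. Earliest persistent-positive visit.** The Week 1 sample is baseline, so the pair must be two later samples at least 16 weeks apart.
- N+I, nivolumab ADA: Week 4 to 25 (21 weeks). Week 10 to 25 is only 15 weeks, so a first positive at Week 10 or 13 needs Week 37.
- N+I, ipilimumab ADA: Week 4 to 25 only. Sampling ends at Week 25, so a first positive at Week 10 or 13 cannot qualify on schedule.
- XELOX: Week 4 or 13 to 31.
- FOLFOX: Week 3, 5, 13 or 17 to 33 (17 to 33 is exactly 16 weeks).

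Dose delays shift actual visit dates. Whatever the delays, the floor is the first post-baseline sample plus 16 weeks: Week 19 (3 + 16) for FOLFOX and Week 20 (4 + 16) otherwise.

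**Step 3. Check the plan's hazards.** For control OS (0.036, 0.06, 0.08 and 0.05 per month, changing at 3, 6 and 24 months), cumulative hazard at 6 months = 3 × 0.036 + 3 × 0.06 = 0.288. The median is 6 + (0.693 − 0.288)/0.08 = 11.06 months, against 11.1 stated in SAP 5.2.

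**Step 4. Deaths before persistence can be shown.** Months = (week − 1) × 7/30.4375. For nivolumab plus chemotherapy (N+C) the OS hazard after 6 months is 0.08 × 0.65 = 0.052 (SAP Table 5.2.1-3). N+I hazards are from SAP Table 5.2.2-1.
- XELOX, Week 31 = 6.90 months: H = 0.288 + 0.90 × 0.052 = 0.335; S = 0.716; 28% dead.
- FOLFOX, Week 33 = 7.36 months: H = 0.288 + 1.36 × 0.052 = 0.359; S = 0.699; 30% dead.
- N+I, Week 25 = 5.52 months: H = 3 × 0.099 + 2.52 × 0.054 = 0.433; S = 0.649; 35% dead.

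These shares are of all subjects. Survival to the first post-baseline sample is 0.975 (XELOX), 0.984 (FOLFOX) and 0.934 (N+I). Among subjects alive then, 1 − 0.716/0.975 = 27%, 1 − 0.699/0.984 = 29% and 1 − 0.649/0.934 = 31% die before the earliest persistent-positive visit.

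**Step 5. Illustrative bias in an OS hazard ratio.** Simulation used 400,000 subjects per scenario and the plan's OS hazards. Assumptions not in the documents: 10% ADA-positive from the first post-baseline sample and staying positive, status independent of outcome, sampling until death. Censoring was spread over 12 to 37.4 months. That is shorter than the follow-up planned for N+I, so the N+I figure is a guide only.

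| Comparison | No ADA effect | True HR 1.5 seen as | True HR 2.0 seen as | Landmark at earliest visit (true 1 / 1.5 / 2.0) |
|---|---|---|---|---|
| N+I | 0.54 | 0.76 | 0.96 | 1.00 / 1.50 / 2.02 |
| N + XELOX | 0.64 | 0.89 | 1.12 | 1.00 / 1.48 / 2.00 |
| N + FOLFOX | 0.62 | 0.85 | 1.06 | 1.01 / 1.50 / 1.98 |

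Under the same assumptions, any-ADA-positive vs ADA-negative gives 0.99 to 1.01 when there is no effect.

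**The case against.** **No hazard ratio by ADA status is planned.** Efficacy is to follow the safety approach, which is incidence tables when numbers allow (for example at least 10 subjects) and individual listings otherwise. The only committed efficacy display is a swimmer plot, which shows ADA timing subject by subject. Immunogenicity is exploratory (SAP 4.3.5), every ADA category is tabulated, the 16-week rule has a stated rationale, and an any-ADA-positive analysis is allowed. All of this stands and limits the severity. It does not remove the problem, because the contrast that the SAP calls primary is the biased one and the alternative is optional.

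**A reader might infer that anyone who progresses or stops treatment early cannot be persistent-positive.** On the plan's PFS hazards, 48% to 61% of N+C subjects have progressed or died by Weeks 31 to 33. The documents do not support using that figure. After nivolumab stops, N+C subjects are still due two scheduled samples: one last sampled on drug at Week 4 (XELOX) is due at Weeks 13 and 31, and one last sampled on drug at Week 13 (FOLFOX) is due at Weeks 17 and 33. Protocol 4.5.1.6 also permits treatment beyond progression. The firm requirement in N+C is to be alive and sampled, so the OS figures are the ones to use. PFS-based figures apply only if sampling in fact ends at progression.

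**A reader might also infer that the safety contrast hides ADA-related reactions.** That is too strong. Only Grade 3 or 4 reactions force discontinuation, some of those N+C subjects can still qualify as persistent-positive, and longer exposure raises cumulative event incidence in persistent-positive subjects. Relevant cases can drop out of the contrast, but the net direction is not known.

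**Sampling is sparse.** The XELOX gap from Week 13 to 31 is 18 weeks, so ADA onset is known only coarsely. This limits any time-dependent analysis.

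**Conclusion.** The concern holds for efficacy. Any OS, PFS or response comparison of persistent-positive with ADA-negative subjects carries immortal-time bias in favour of persistent-positive, and it can mask a loss of efficacy. The direction follows from the definitions and the sampling schedule, whatever the ADA rate.

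The size rests on assumptions. The shares dead before persistence can be shown (28% to 30% in N+C, 35% in N+I) come from the plan's own hazards and scheduled visits. The null OS hazard ratios of 0.54 to 0.64 also depend on an assumed ADA rate and onset pattern, and they describe an analysis that the SAP implies but does not specify. In N+I, where no sampling after discontinuation is stated, deaths alone may understate the selection.

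For safety, the supportable statement is that some early-stopping ADA-positive subjects leave the main contrast, with uncertain net effect. No conclusion that ADA lacks clinical impact is pre-specified. Severity is minor to moderate.

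**What to change.** Amend SAP 7.6.13 as follows:
- **Efficacy.** For any comparison by ADA status, start follow-up at a landmark among subjects still at risk, with status fixed by then. Suitable landmarks are Week 31 (XELOX), Week 33 (FOLFOX), Week 25 for ipilimumab ADA, and Week 25 or 37 for nivolumab ADA in N+I. Alternatively, treat ADA status as time-dependent.
- **Main contrast.** Make any-ADA-positive vs ADA-negative a committed comparison, subject to the same timing rule for efficacy. Keep persistent-positive as a descriptive row.
- **Hypersensitivity and infusion reactions.** Report all ADA-positive categories, with event timing relative to the first positive sample.

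The cost is SAP wording and modest programming. A landmark analysis uses fewer subjects, and the sampling gaps leave ADA onset coarse under either method. The SAP document history shows that the first N+C report is already written, so the change applies directly to the N+I report at the second analysis time point and to N+C as a supplementary analysis.
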